3.5.6.2 Potential serious hepatotoxicity

Potential serious hepatotoxicity will be analyzed for the MAD, LTE, and Active Treatment Period. Potential serious hepatotoxicity is defined as a confirmed ALT or AST > 3x ULN and confirmed total bilirubin > 2x ULN at any time post-baseline in the analysis period, not necessarily concurrent. A scatterplot of the maximum post-baseline ALT or AST value relative to ULN and maximum post-baseline total bilirubin value relative to ULN (not necessarily concurrent) for each subject will be provided. A spaghetti plot of ALT, AST, ALP and total bilirubin values over time for subjects with potential serious hepatotoxicity will be provided. In addition, subjects with ALT > 1x ULN, >3x ULN, >5x ULN, >10x ULN or >20x ULN, subjects with AST > 1x ULN, >3x ULN, >5x ULN or >20x ULN, subjects with total bilirubin >1x ULN or >2x ULN, subjects with ALP >1x ULN or >1.5x ULN, and subjects with AST or ALT > 3x ULN post-baseline accompanied by concurrently elevated total bilirubin >1.5x ULN or >2x ULN will be presented. Concurrent is defined as on the same day. A listing of subjects with potential serious hepatotoxicity will be provided.

A confirmed value is based on a consecutive lab value performed on a different day to, but within 7 days of, the initial value. If the consecutive value is in the same or worse ULN criteria described above, then the initial value is confirmed. If there is no retest within 7 days, then the initial value is presumed confirmed. If there are multiple results on the same day (no matter from the same lab vendor or different lab vendors), then the worst value will be utilized in the analysis.

3.5.7 Vital Signs Measurements

Vital signs will include heart rate, respiratory rate, body temperature, body weight, seated and standing systolic and diastolic blood pressure and pulse, and orthostatic changes.

Orthostatic changes include 3 variables: change from seated systolic blood pressures to average of all available standing systolic blood pressures, change from seated diastolic blood pressure to average of all available standing diastolic blood pressure, and change from seated heart rate to average of all available standing heart rate.

Summary tables will be created for the MAD and LTE Periods separately to present the descriptive statistics for vital sign values as well as the change and percent change from baseline at each post-baseline visits.

3.5.8 12-Lead Electrocardiograms (ECG)

Safety 12 lead ECG will be performed in triplicate at the visits indicated in the protocol Schedule of Procedures. ECG data will be collected through a central reader.

The ECG data will include ventricular rate (VR), PR interval, QRS duration, QT, QTcF (QT corrected using the Fridericia's formula), and QTcB (QT corrected using the Bazett's formula).

QTcF and QTcB will be calculated based on the subject's reportable ECG data at each time point using the formula described below:

QTcF = QT / (RR)
$$^{1/3}$$
, where RR = 60 / VR

$$QTcB = QT / (RR)^{1/2}$$
, where $RR = 60 / VR$

At Screening visit, three replicates of ECG parameters will be recorded, and the mean from all replicates will be used as the patient's reportable value at Screening visit. Only calculated QTcB and QTcF will be summarized and included in the data listing. The QTC value recorded on the CRF will not be summarized and will be excluded from the data listing.

For the continuous variables, the average of measurements at a given visit will be used for analysis. For overall interpretation, the worst categorical results of triplicate results and the associated findings will be used for analysis. Summary tables will be created for the MAD and LTE Period respectively to present the descriptive statistics of the actual values, the change and percent change from baseline at each study visit for continuous variables above; and counts and percentages at each study visit for categorical responses to overall interpretation.

Criteria for potentially clinically significant used to define post-Baseline QTcB and QTcF categorization are as follows: \leq 450 msec, >450 msec to \leq 480 msec, >480 msec to \leq 500 msec and >500 msec for measured values as well as >30 msec and >60 msec for changes from Baseline. The number and percentage of subjects reporting a category will be presented by treatment group, separately for QTcB and QTcF. Subjects will be counted only once if they had more than one such event during the analysis period, so only a subject's worst post-Baseline value will be considered.

All the ECG data collected in triplicate, except the CRF QTC value, will be listed.

3.5.9 Physical and Neurological Examinations

The physical & neurological examinations for the MAD and MAD+LTE Periods will be provided in patient listings.

3.5.10 Safety Neuroimaging Assessments

MRI safety sequences (T2 FLAIR, GRE T2 star, T2 Fast Spin Echo [FSE]/Turbo Spin Echo [TSE], Diffusion Tensor Imaging [DTI]) will be performed to characterize the patients' pretreatment and post-treatment state, at Screening and Day 169 (post-treatment period) in Part 1, and at the Registration Visit (patients who are not seamlessly transitioning only), at Day 252 (or Day 336 if not performed at Day 252) and Day 449 (post-treatment period) in Part 2.

Safety MRI will be summarized for the MAD Period, LTE Period and Active Treatment Period by analysis group. During the MAD Period, the number of subjects with an increased number of microhemorrhages at Day 169 in comparison to baseline, and the number of subjects with an increased white matter disease total score at Day 169 in comparison to baseline will be

presented. Treatment-emergent (TE) brain MRI abnormalities are those occurring at Day 169 which are new (were not present at baseline) or which are worsening (were present at baseline and have a status of 'still present and increased in size' at Day 169). The number of subjects with any TE brain MRI abnormality will be summarized, as well as those with any new TE brain abnormality, and with any worsening TE brain MRI abnormality. The number of subjects with a specific type (e.g., macrohemorrhages) of new abnormality will be presented; similarly, the number with a specific type of worsening abnormality will be presented. During the LTE Period, similar analysis will be performed by analysis group at Registration Visit Part 2, Day 252 Part 2 (or Day 336 if not performed at Day 252 Part 2), and Day 449 Part 2. During the Active Treatment Period, similar summaries will be conducted by analysis group at Day 169 Part 1, Registration Visit Part 2, Day 252 Part 2 (or Day 336 if not performed at Day 252 Part 2), and Day 449 Part 2.

Safety MRI for the MAD Period and the MAD+LTE Period will be presented in data listings.

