For patients who terminate early from the Treatment Evaluation Period in Part 1 for reasons other than withdrawal of consent and are not willing to participate in the Post-Treatment Period, every effort should be made to (a) conduct the full block of visits associated with the last dose received (see description of "visit blocks" above), (b) conduct the visit scheduled for 7 days after the last dose received and (c) conduct the Week 37 visit as an Early Termination Visit. Patients who prematurely discontinue the Treatment Evaluation Period, or the Post-Treatment Period, in Part 1 will not be allowed to participate in Part 2.

For patients withdrawn from the study during the Treatment Evaluation Period in Part 2 for reasons other than withdrawal of consent, every effort should be made to encourage the patient to (a) conduct the full block of visits associated with the last dose of ISIS 814907 that would have been received had the patient not withdrawn (see description of "visit blocks" above), (b) conduct the visit scheduled for 7 days after the last dose received, and (c) proceed to the

Week 60 visit approximately 4 weeks after last dose and conduct the next visit in the Post-Treatment Period at Week 64 (see Appendix A).

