Appendix A A.1. Schedule of Procedures – MAD Part 1, 4-Dose Regimen, Cohorts A and B Continued

| Study Period | Screen | | | | | | | Tr | eatn | | Evalu 3 We | | Peri | od | | | | | | | | Post | | ment Po /eeks) | eriod |
|---|--------------|----|----|----|----|-----|----|-----|------|----|---------------|----|------|----|----|-----|----|----|----|----|-----|-----------------|-----|-------------------|--------------------------|
| Week | -8 to -1 | | | 1 | | 2 | | 5 | | | 6 | | 9 |) | | 10 | | 1; | 3 | | 14 | 17 ¹ | 21 | 25 | 37 or ET ¹ |
| Day | -57 to -2 | -1 | 1 | 2 | 3 | 8 | 28 | 29 | 30 | 31 | 36 | 56 | 57 | 58 | 59 | 64 | 84 | 85 | 86 | 87 | 92 | 113 | 141 | 169 | 253 |
| Visit Window (days)* | - | | | 0 | | ± 3 | | ± 3 | 3 | | ± 3 | | ± | 3 | | ± 3 | | ± | 3 | | ± 3 | ± 3 | ± 7 | ± 7 | ± 7 |
| Visit Type ² | cl | cl | cl | cl | ph | cl | cl | cl | cl | ph | cl | cl | cl | cl | ph | ph | cl | cl | cl | ph | ph | cl | cl | cl | cl |
| Structural MRI, safety MRI (GRE T2 star, T2 FLAIR, T2 FSE/TSE, DTI) and ASL | х | | | | | | | | | | | | | | | | | | | | | | | X | |
| Imaging of CSF space | Х | | | | | | | | | | | | | | | | | | | | | | | | |
| FAQ, NPI-Q | Х | Χ | | | | | | | | | | | | | | | | | | | | Х | | Χ | Х |
| RBANS ⁹ | Х | Х | | | | | | | | | | Χ | | | | | | | | | | Х | | Х | Х |
| MMSE ⁹ | Х | | | | | | | | | | | Χ | | | | | | | | | | Х | | Х | Х |
| MHIS, CDR, GDS-SF | Х | | | | | | | | | | | | | | | | | | | | | | | | |
| C-SSRS | Х | Χ | Х | | | Х | Х | Х | Χ | | Х | Х | Χ | Х | | | Χ | Х | Χ | | | Х | Χ | Χ | Х |
| Serum/Plasma Biomarker Sample | | Х | | | | | Х | | | | | Х | | | | | Х | | | | | Х | Х | Х | Х |
| Thyroid Panel | Х | | | | | | | | | | | | | | | | | | | | | | | | |
| PT, INR, aPTT | Х | Χ | | | | | Х | | | | | Х | | | | | Χ | | | | | Χ | Х | Χ | Х |
| Archived Serum Sample ¹⁰ | | Х | | | | | Х | | | | | Х | | | | | Х | | | | | Х | Х | Х | Х |
| Drug/Alcohol Screen | Х | | | | | | | | | | | | | | | | | | | | | | | | |
| ECG (12-Lead, triplicate) | Х | Χ | | Χ | | | Χ | | | | | Χ | | | | | Χ | | | | | Χ | | | Х |
| Adverse Events | Х | Χ | Χ | Χ | Х | Х | Χ | Χ | Χ | Χ | Χ | Χ | Χ | Х | Χ | Χ | Χ | Χ | Χ | Х | Х | Χ | Х | Χ | Х |
| Prior/Concomitant Therapy/Procedures | Х | Х | Х | Х | Х | Х | Х | Х | Χ | Х | Х | Х | Х | Х | Х | Х | Х | Х | X | Х | Х | Х | Х | Х | Х |

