Appendix A A.4. Schedule of Procedures – LTE Part 2, All Cohorts Continued

| Study Period | | ment Period |
|--|-------|-----------------------|
| | (16 V | Veeks) |
| Week | 60 | 64 or ET ¹ |
| Day | 421 | 449 |
| Visit Window (days)* | ± 3 | ± 7 |
| Visit Type ² | cl | cl |
| ISIS 814907 Administration | | |
| Overnight Stay ⁴ | | |
| Informed Consent | | |
| Inclusion/Exclusion | | |
| Medical History ⁵ | | |
| Body Weight | | X |
| Physical & Neurological Exam ⁶ | Х | Х |
| Vital Signs (BP, HR)7, (RR, T) | Х | X |
| Orthostasis Assessment | | X |
| Chemistry Panel | X | X |
| Hematology | X | X |
| Urinalysis | Х | X |
| Structural MRI, safety MRI (GRE T2 star, | | X |
| T2 FLAIR, T2 FSE/TSE, DTI) and ASL | | , |
| FDG-PET or Tau PET8 | | X |
| FAQ, NPI-Q | | X |
| RBANS ⁹ | | X |
| MMSE ⁹ | | X |
| MHIS, GDS-SF | | |
| CDR | | X |
| C-SSRS | Х | Х |
| PT, INR, aPTT | Х | X |
| Local PT, INR, aPTT, platelets ¹⁰ | Χ | X ¹² |

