3.2.4 Analytical visits

All post-baseline data will be summarized using the visit labels provided in the data. Multiple results with the same visit label will be averaged for the continuous variables, and the worst result will be used for the categorical variables. Results with visit labels as "Unscheduled" will be presented in data listing, but not be included in the by-visit summary tables and figures, except for determining baseline.

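### The treatment-emergent MRI counts use named visits only, so an abnormality seen only on an off-schedule post-dose scan is listed but not counted, and the number of patients with no post-baseline scan is not reported

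*Combined protocol and SAP*

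**What the plan says.** **Definition.** For the MAD Period, SAP 3.5.10 states: "Treatment-emergent (TE) brain MRI abnormalities are those occurring at Day 169 which are new" (absent at baseline), or present at baseline and larger at Day 169. The microhemorrhage summary uses the same visit: "the number of subjects with an increased number of microhemorrhages at Day 169 in comparison to baseline". So does the white-matter score. In the LTE Period the counts are made at the Registration Visit, at Day 252 (or Day 336 if Day 252 was missed) and at Day 449. The Active Treatment Period uses those visits plus Part 1 Day 169. Safety MRI data are also listed.

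**Unscheduled results.** SAP 3.2.4 says: "Results with visit labels as 'Unscheduled' will be presented in data listing, but not be included in the by-visit summary tables and figures". The only exception is for determining baseline.

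**Scan schedule.** In protocol Appendix A.1 the row "Structural MRI, safety MRI (GRE T2 star, T2 FLAIR, T2 FSE/TSE, DTI) and ASL" is marked at Screening and Day 169 only. The same row in A.2 and A.3 has the same two marks. The column for Week 37 or early termination (ET) is empty in all three. In A.4 (Part 2) the MRI row is marked at Week 64 or ET.

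**Early leavers.** Under protocol 8.9, patients who stop in the Part 1 Treatment Evaluation Period and will not take part in the Post-Treatment Period are asked to finish the visit block and the 7-day visit, then "conduct the Week 37 visit as an Early Termination Visit". Appendix A footnote 1 sends those who leave the Post-Treatment Period early to the same visit. Protocol 8.8.1 bars both groups from Part 2.

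**The concern.** Safety is the primary objective, and safety MRI is a listed safety endpoint in protocol 10.1.1 and SAP 1.3.1. The MRI table is where a reader will look for the number of patients per dose group with a new or worsening lesion. As defined, that number reflects only what is visible on particular days. A lesion found on an extra scan between doses, and no longer visible or not rescanned at Day 169, is absent from it.

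The definition is also out of step with the rest of the SAP's safety section, which otherwise asks whether a patient ever had the finding after baseline. No reason is given for treating MRI differently.

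A second gap lies beside it. Some patients may have no post-dose scan at all, and SAP 3.5.10 neither states its denominator nor plans to report how many such patients there are.

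**Working it through.** The plan states no sample size, power or error rate for the MRI endpoint, so there is no plan figure to reproduce. The check is a comparison of texts, with simple arithmetic for scale.

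**1. Timing.** Last Part 1 dose on Day 85 (both regimens); counted scan on Day 169. 169 − 85 = 84 days.

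**2. How other safety outcomes are counted in the SAP.**

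| Outcome | SAP section | Data that count |
|---|---|---|
| C-SSRS | 3.5.5 | a yes response at any time after baseline |
| Laboratory shifts | 3.5.6 | minimum and maximum post-baseline values |
| Hepatotoxicity | 3.5.6.2 | any time after baseline in the period |
| QTc categories | 3.5.8 | worst post-baseline value |
| Brain MRI | 3.5.10 | named visits only |

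**3. Who lacks a scheduled post-dose scan in Part 1.**

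- Stops dosing but stays in follow-up: goes to Week 17 and then all Post-Treatment visits (Appendix A, footnote 1), so the Day 169 MRI is scheduled.
- Has a dose-limiting toxicity: should complete the Post-Treatment Period (protocol 3.8), so the scan is scheduled.
- Leaves between Day 169 and Day 253: already past the scheduled scan.
- Leaves before Day 169 and declines follow-up: goes to the Week 37/ET visit, which has no MRI, and cannot enter Part 2. No post-dose scan is scheduled.

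**4. Weight of one patient.** Active patients per cohort are the sentinel active patient plus the remaining active allocation: 1 + 5 = 6 (A), 1 + 5 = 6 (B), 1 + 8 = 9 (C), 1 + 11 = 12 (D). The total is 33 active, leaving 44 − 33 = 11 on pooled placebo. One uncounted event is 1/6 = 16.7%, 1/6 = 16.7%, 1/9 = 11.1% or 1/12 = 8.3% of the group.

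**5. Effect of the unstated denominator.** Take a group of 6 with one event and one unscanned patient. Over all treated patients the rate is 1/6 = 16.7%; over scanned patients it is 1/5 = 20.0%. In the first case the unscanned patient is treated as event-free. SAP 3.4.2 imputes nothing and does not settle the choice.

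**6. Chance of seeing at least one event, for scale.** Formula: 1 − (1 − p)^(n − m), with n patients, m missing scans and an assumed event rate p. The documents give no rate.

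| n | p | m = 0 | m = 1 | m = 2 |
|---|---|---|---|---|
| 6 | 5% | 26.5% | 22.6% | 18.5% |
| 6 | 10% | 46.9% | 41.0% | 34.4% |
| 6 | 20% | 73.8% | 67.2% | 59.0% |
| 12 | 10% | 71.8% | 68.6% | 65.1% |

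**The case against.** The strongest defence is that little is lost from the safety record as a whole. Off-schedule findings are listed. A symptomatic lesion would be expected as an adverse event, and SAP 3.5.3 counts those without regard to visit label. Protocol 10.6.2 provides narratives for serious and significant events. The FSMG sees unblinded data throughout. One scan per patient at a common visit also gives equal ascertainment across groups, which symptom-triggered scans would not. All of this stands. It is why the scheduled-visit rows should stay and why the gap lies in one table. It does not explain why that table should omit a post-dose lesion known to the sponsor.

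The off-schedule scan is also hypothetical. The protocol schedules no symptom-prompted MRI. For an event suggesting cognitive or motor dysfunction, Appendix A calls for a neurological examination, RBANS and MMSE. Protocol 6.1 allows extra visits for a reported adverse event without naming MRI. Such scans are possible, but their number is unknown.

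Three stronger readings are not supported:

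- A reader might infer that everyone who ends Part 1 treatment early goes unscanned. Those who remain in follow-up, including patients with a dose-limiting toxicity, are scheduled for Day 169.
- A reader might infer that the MRI rate is biased downward. The denominator is unstated, and if it is scanned patients, an unscanned patient does not mechanically lower the rate. Downward bias is plausible but not shown.
- A reader might put a number on the unscanned, for example 5–15% of 44, or about 2 to 7 patients. Nothing in the documents supports that dropout range.

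The contrast with Part 2 is also weaker than it looks. MRI sits in the Week 64/ET column because Day 449 is itself a planned MRI visit.

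**Conclusion.** The point holds in a limited form. The treatment-emergent MRI counts, as defined, would omit a new or worsening abnormality seen only on an off-schedule post-dose scan, while the SAP's rules for C-SSRS, laboratory shifts, hepatotoxicity and QTc use any or worst post-baseline data. The finding would be missing from the MRI counts, not from the report. Separately, patients who leave Part 1 before Day 169 and decline follow-up have no scheduled post-dose MRI, and the plan does not report how many they are.

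One event is 8.3 to 16.7 percentage points of a planned active group, assuming the cohorts fill as planned. How many patients either gap affects cannot be determined from the documents. The detection probabilities above rest on assumed event rates and serve only for scale. The change is worth making because safety is the primary objective, the groups are small and the correction needs no new data.

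**What to change.** In SAP 3.5.10, for each analysis period:

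- Add a per-patient count of new or worsening MRI abnormalities on any post-baseline scan in the period, unscheduled scans included, with each patient classed by worst finding.
- Keep the scheduled-visit rows alongside.
- Flag events that come from off-schedule scans, because ascertainment and time since dose differ.
- State the denominator for the new count as patients with at least one post-baseline scan, and report the number per group with none.

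The cost is about one sentence of SAP text and one extra table row, plus the count of unscanned patients, all from data already collected. The drawback is unequal ascertainment, which the flag and the retained visit rows make visible.

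A safety MRI at the Part 1 ET visit (Appendix A.1–A.3) is optional. It would be an added procedure, and about 4 weeks after the last dose its timing would differ from the 84 days of the Day 169 scan. It matters only if Part 1 visits are still open. The SAP already describes Part 1 enrollment and Cohort D regimen selection in the past tense, so for the ET gap, reporting the number unscanned is probably the only remedy left.

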3.2.2.2 LTE Period, MAD+LTE Period, and Active Treatment Period

The following analysis groups will be used for the LTE Period, MAD+LTE Period, and Active Treatment Period unless otherwise indicated. In case of very few subjects in any group, the analysis groups may be further pooled.

- Late Start A+B+C: MAD Cohorts A, B and C placebo-treated patients
- Late Start D: MAD Cohort D placebo-treated patients
- Early Start A: MAD Cohort A ISIS 814907-treated patients
- Early Start B: MAD Cohort B ISIS 814907-treated patients
- Early Start C: MAD Cohort C ISIS 814907-treated patients

- Early Start D: MAD Cohort D ISIS 814907-treated patients
- ISIS 814907 60 mg Q12W (LTE Period and Active Treatment Period):
 - LTE Period: All MAD Cohort A, B, and C roll-over subjects, regardless of randomization assignment. This group will be included for select analyses only in the LTE Period, e.g., AE and SAEs, safety analyses (except shift analyses for laboratory assessments), selected exploratory analyses only (including MRI volumetric, PET and clinical evaluations), PD and PK analyses.
 - Active Treatment Period: All MAD Cohort A, B, and C subjects, regardless of either randomization assignment or LTE enrollment status. This group will be included for select analyses only in the Active Treatment Period, e.g., serious TEAEs potentially related to Study Drug, overall summary of TEAEs, and safety MRIs.
- All Roll-over (LTE Period only, excluding PK analyses): All MAD Cohorts ISIS 814907-treated and placebo-treated roll-over patients.
- ISIS 814907 115 mg Q12W (LTE Period and Active Treatment Period): All MAD
 Cohort D roll-over subjects, regardless of randomization assignment (LTE Period). All
 MAD Cohort D subjects, regardless of either randomization assignment or LTE
 enrollment status (Active Treatment Period).
- Total Active (Active Treatment Period only, excluding PK analyses): All patients who receive at least 1 dose of ISIS 814907 in either the MAD or LTE periods.

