3.2.3.2 Active treatment period baseline

Active treatment period baseline will be used to analyze the LTE Period and the Active Treatment Period. Active treatment period baseline is the same as the MAD baseline for early start subjects, and for late start subjects is the last non-missing measure collected prior to the first dose of study drug in the LTE except in the instances below:

- o For vital signs (blood pressure [BP] and heart rate [HR]), as the average of the triplicate values collected on Day 1 pre-dose in the LTE. If only one or two assessments are available, the single assessment or average of the two assessments will be used.
- For ECG continuous parameters, as the average of the triplicate values collected immediately prior to first dose in the LTE. For ECG interpretation, baseline will be defined as the worst categorical results of the triplicate results collected immediately prior to first dose in the LTE.
- For C-SSRS suicidal ideation score, as the maximum score collected on Day -1 and Day 1 pre-dose in the LTE.

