3.7.3.5 Clinical Dementia Rating (CDR) Scale

The CDR is a global scale used at Screening to categorize the severity of Alzheimer's type dementia. It is used to rate the patient's cognitive performance in 6 domains: memory,

orientation, judgment and problem solving, community affairs, home and hobbies, and personal care. Categorical scores for each domain are 0 (none), 0.5 (questionable), 1 (mild), 2 (moderate) and 3 (severe). A summed total score (CDR Sum of Boxes [CDR-SOB]) is produced, and a global score (using the same 5 grades of dementia) is derived. CDR are collected at Screening (all cohorts), Registration/Part 2 (Cohorts A and B only) and Day 449/Part 2 (all cohorts).

In the MAD period, the CDR-SOB at Screening will be summarized as baseline characteristics.

In the LTE and MAD+LTE Periods, CDR-SOB, global score and subdomain scores (actual value, absolute change and percent change from baseline) will be summarized by analysis group and each post-baseline visit at Registration visit (for Cohorts A and B only) and at Day 449 visit.

All CDR collected scores will be presented in data listings for the MAD and MAD+LTE Periods.

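### The LTE safety-MRI and CDR tables treat the Registration visit as post-baseline, though it precedes the first LTE dose and is the late-start Cohort A/B patients' own baseline

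*Combined protocol and SAP*

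**What the plan says.** SAP 3.5.10 defines the safety-MRI summary for Part 1 as a comparison with baseline: increases in microhemorrhages, increases in the white matter score, and treatment-emergent findings. On the last of these it says "Treatment-emergent (TE) brain MRI abnormalities are those occurring at Day 169 which are new (were not present at baseline", and it adds findings already present that have grown. It then extends the analysis: "During the LTE Period, similar analysis will be performed by analysis group at Registration Visit Part 2", followed by Day 252 (or Day 336) and Day 449. The Active Treatment Period gets the same visits plus Part 1 Day 169.

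For CDR in the LTE and MAD+LTE Periods, SAP 3.7.3.5 says that scores and changes "will be summarized by analysis group and each post-baseline visit at Registration visit (for Cohorts A and B only) and at Day 449 visit".

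The baseline rule is in SAP 3.2.3.2: "Active treatment period baseline will be used to analyze the LTE Period and the Active Treatment Period". It continues "Active treatment period baseline is the same as the MAD baseline for early start subjects", while the baseline "for late start subjects is the last non-missing measure collected prior to the first dose of study drug in the LTE". The listed exceptions are vital signs, ECG and C-SSRS; MRI and CDR are not among them.

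SAP 3.2.2.2 defines the LTE Period 60 mg Q12W group as "All MAD Cohort A, B, and C roll-over subjects, regardless of randomization assignment", and uses it for safety analyses and clinical evaluations. The All Roll-over group adds Cohort D.

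**The concern.** A visit held before the first LTE dose is analysed as if it followed baseline. For late starters in Cohorts A and B it is the baseline, so the row compares a value with itself. For early starters in the same cohorts the change is real, but it belongs to the Part 1 regimen and the interval after it, not to 60 mg Q12W.

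Safety is the primary objective, and the safety MRI sequences are a listed safety endpoint (protocol 10.1.1, SAP 1.3.1). A table that can show treatment-emergent brain MRI findings under a 60 mg Q12W heading before that regimen began, beside a late-start row fixed at zero, invites misattribution.

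**Working it through.** The plan gives no figure to reproduce here: it states no statistical rationale for the sample size, and the LTE summaries are descriptive. The check applies the SAP's baseline rules to the Registration record and counts planned patients.

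**Timing.** The protocol's Part 2 schema and Appendix A.4 place Registration at Days -21 to -2. Protocol 6.1.2.1 limits it to Cohorts A and B. In Appendix A.4, MRI and CDR are scheduled at Registration and not again before the Day 1 dose.

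**Baseline by start group, LTE and Active Treatment Periods.**
- Late start A/B: the last value before the first LTE dose is the Registration value. Change = Registration − Registration = 0, and no MRI finding can be new or worse. The one exception is an unscheduled assessment between Registration and Day 1, because SAP 3.2.4 lets unscheduled results set baseline.
- Early start A/B: the baseline precedes Part 1. Change = Registration − MAD baseline. This follows four doses of 10 or 30 mg and an off-drug interval. The last Part 1 dose is Day 85 and the last Part 1 visit Day 253, so 253 − 85 = 168 days (24 weeks) pass on the planned schedule before the variable gap begins.
- Cohorts C and D: no Registration visit.

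**Baseline in the MAD+LTE Period.** SAP 3.2.3.1 uses the MAD baseline for everyone, so Registration is validly post-baseline for CDR there.

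**Planned counts** (protocol 3.1.1; 3:1 allocation; full roll-over):

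| Cohort | N | Early start | Late start | Registration visit |
|---|---|---|---|---|
| A | 8 | 6 | 2 | yes |
| B | 8 | 6 | 2 | yes |
| C | 12 | 9 | 3 | no |
| D | 16 | 12 | 4 | no |

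- 60 mg Q12W column: 8 + 8 + 12 = 28 patients, of whom 16 have a Registration record (12 early, 4 late).
- Late Start A+B+C: 2 + 2 + 3 = 7 patients, of whom 4 have a Registration record, all forced to zero.
- Share of forced zeros among Registration records: 4/16 = 25%.

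**Dilution of the row.** Let p be the early-start A/B rate of new or worsening MRI findings at Registration. The 60 mg Q12W column shows (12p + 4 × 0)/16 = 0.75p if the denominator is patients with a record, or 12p/28 = 0.43p if it is the column total. The SAP does not say which. The values of p below are assumptions, shown for range:

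| Assumed p | Denominator 16 | Denominator 28 |
|---|---|---|
| 10% | 7.5% | 4.3% |
| 20% | 15.0% | 8.6% |
| 30% | 22.5% | 12.9% |
| 50% | 37.5% | 21.4% |

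A mean CDR change over the 16 patients with a record is likewise 0.75 times the early-start mean. With e early and l late starters actually returning, the factor is e/(e + l). In the All Roll-over column the factor is 0.75 over patients with a record, or 12/44 = 0.27 for an MRI rate over all planned patients.

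In every case the non-zero part of the row arose before any A/B patient received 60 mg Q12W.

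**The case against.** The strongest reply is that the zeros need never be printed. SAP 3.2.4 summarises post-baseline data, and a visit that serves as a patient's baseline is not post-baseline for that patient, so a programmer could leave late starters out. That is sensible practice, but the SAP does not say it. Both sections name Registration with no exclusion by start group, whereas SAP 3.5.6.1 does separate early and late starters for laboratory abnormalities. Leaving late starters out also would not cure the pooled column, which would still show pre-60 mg findings under a 60 mg Q12W label.

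Several points on the other side stand:
- The CDR sentence covers the LTE and MAD+LTE Periods together, and it is correct for the latter.
- The term post-baseline is literal only for CDR. For MRI it follows from applying the same comparison with baseline at that visit.
- A reader might infer that the whole row is pre-treatment change. It is not: early-start A/B patients were treated in Part 1, and their Registration value is a valid post-baseline result in their own columns.
- A reader might infer that the early-versus-late contrast always disfavours early start. It need not: CDR can be unchanged or improve, and an early-start MRI count can be zero. No test of that contrast is specified at this visit.
- Early starters keep the MAD baseline at Day 252/336 and Day 449 as well, so those rows also accumulate change from before 60 mg dosing. That is an explicit choice in the SAP, and removing Registration everywhere would hide what was already present when 60 mg began.
- The visit label, the separate start-group columns and the patient listings limit the risk of misreading.

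**Conclusion.** The concern holds. As written, the Registration row in the LTE Period (MRI and CDR) and in the Active Treatment Period (MRI) is zero by construction for late-start A/B patients: 4 planned, out of 11 planned placebo patients in all. In the pooled LTE columns it mixes those zeros with changes in 12 planned early-start patients that predate 60 mg Q12W.

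The dilution has no single value. The factors 0.75 and 0.43 for the 60 mg Q12W column assume full roll-over, complete Registration data and zeros entered for late starters; they differ only in the denominator. The forced zero assumes no unscheduled MRI or CDR between Registration and LTE Day 1.

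The damage is confined to interpretation of one row of descriptive tables, including a listed safety endpoint. No test or sample size depends on it, and the later visits are unaffected. The documents do not support a claim that the early-start results at Registration are invalid or that the row should be removed for every group.

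**What to change.** Amend SAP 3.5.10 and 3.7.3.5 as follows.
- In the LTE and Active Treatment Periods, treat Registration as baseline only for late starters and omit them from the Registration change row.
- In the LTE Period, omit the Registration row from the pooled 60 mg Q12W and All Roll-over columns.
- In the Active Treatment Period, exclude late starters' Registration records from every pooled column. SAP 3.2.2.2 assigns safety MRI to a 60 mg Q12W group in that period, but Table B3 has no such column; reconcile the two.
- Keep Registration in the Early Start A and B columns, labelled 'before first LTE dose'.
- Keep Registration for all A/B patients in the MAD+LTE Period, where the MAD baseline applies.
- State the denominator for visits that only some cohorts attend.

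The cost is wording in two sections and a few table shells. No data are lost. Day 252/336 and Day 449 results stay the same, because no baseline value changes.
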